2.3.3 ASSESSMENT OF POTENTIAL RISKS AND BENEFITS

Include an assessment of known potential risks and benefits, addressing each of the following:

- *Rationale for the necessity of exposing participants to risks*
- *A summary of the ways that risks to participants were minimized in the study design*
- *Justification as to why the value of the information to be gained outweighs the risks of participation in the study*

As indicated above, the risks to study participants are small. ISA will protect against any potential risk and ensure the confidentiality of the data using multiple methods. First, to protect against psychological risk or discomfort in completing the survey, participants will be informed of the confidentiality of the surveys (i.e., they will contain no personally identifying information) and the secure nature of the computer-based survey tool. In addition, questions will be phrased in a way to minimize discomfort and participants will be free to skip questions they do not wish to answer. No one outside the study team will have access to the data. Moreover, participants will be told specifically that if, because of reviewing their assigned materials or completing the research surveys, they are feeling distressed about their physical health, they should discuss their concerns with a CACOST Staff Member. They will also be provided with a list of resources in the informed consent that can provide information about diabetes.

To maintain confidentiality of all data collected, no names or other identifying information will be included on the survey, or as part of STEPS or the control materials. As noted earlier, the file that will link the participant name to the user ID and study phone number will be maintained on a password protected computer that will not house the survey data. The only people that will have access to the linking file will be the Principal Investigator and her staff. Finally, we will utilize strict security protocols – described previously – to protect the confidentiality of all information stored on our secure server as part of the STEPS intervention.

To protect against any breaches of confidentiality, all project staff proposed to conduct the data collection have received or will receive training on the protection of research participants and are or will be well

versed in the Code of Federal Regulations (including 45 CFR 46 and 42 CFR) and the Belmont Report. ISA continually obtains information from the Office for Human Research Protections (OHRP) at NIH on new regulations regarding the protection of human subjects, which is disseminated to all staff.

After all participants have completed follow-up surveys, the linking file housed on the ISA computer – the only file that contains participant’s personal information (e.g., name, phone number) – will be deleted. In addition, the Windows Eraser program will be used to completely remove (i.e., “wipe”) the linking file from the computer by overwriting it several times using government-sanctioned deletion algorithms. Deidentified participant research data from the baseline and follow-up surveys will be retained for 3 years from the submission of the final financial report to NIH, in keeping with guidelines described in the NIH Grants Policy Statement.

The Phase II evaluation will provide very important information about the efficacy of the STEPS intervention to improve the health of Hispanic adults residing in rural areas. This data is critical to developing a successful program that can help Hispanic adults reduce their risk of Diabetes. Knowledge gained from this field test will be integrated into the final program prior to marketing to FQHCs and other health care organizations. We believe that the risks associated with this Phase II effort are reasonable in relation to the valuable information we will receive.

3 OBJECTIVES AND ENDPOINTS

Provide a description of the study objectives and endpoints, as well as a justification for selecting the particular endpoints, in the table format included below. This will provide clear articulation of how the selected primary and secondary endpoint(s) are linked to achieving the primary and secondary objectives and an explanation of why endpoint(s) were chosen. Data points collected in the study should support an objective or have a regulatory purpose. Therefore, careful consideration should be given prospectively to the amount of data needed to support the study’s objectives.

*An **objective** is the purpose for performing the study in terms of the scientific question to be answered. Express each objective as a statement of purpose (e.g., to assess, to determine, to compare, to evaluate) and include the general purpose (e.g., feasibility, acceptability, engagement of the intervention target, identifying mechanisms of action, mediation, moderation, efficacy, effectiveness, dissemination, implementation).*

*A study **endpoint** is a specific measurement or observation to assess the effect of the study intervention. Study endpoints should be prioritized and should correspond to the study objectives and hypotheses being tested. Give succinct and precise definitions of the study endpoints used to address the study’s primary objective and secondary objectives (e.g., specific diagnostic tests that define safety or efficacy, clinical assessments of disease status, assessments of psychosocial characteristics, patient reported outcomes, behaviors or health outcomes). A full description of study endpoints, including administration, scoring, psychometrics, adjudication of endpoints, etc., belongs in **Section 8, Study Assessments and Procedures**.*

A putative mechanism of action is the theorized explanation for how the intervention functions.

*Consider whether primary and secondary endpoints should be adjusted for multiple comparisons, family-wise error rates, alpha inflation, etc. Details of any such adjustments should be included in **Section 9.4.2, Analysis of the Primary Endpoint(s)** and **Section 9.4.3, Analysis of the Secondary Endpoint(s)**.*

OBJECTIVES	ENDPOINTS	JUSTIFICATION FOR ENDPOINTS
Primary		
To evaluate whether the intervention increases percent weight loss in Hispanic adults.	
• Weight measured by the research staff at each study visit	Tests causal mechanism
Secondary		
To evaluate whether the intervention improves A1C levels, diabetes knowledge, and improves health behaviors.	
• A1c levels measured by research staff at each study visit• Diabetes knowledge• Eating pattern behaviors• Physical activity behaviors	Tests causal mechanism or potential moderating effects

4 STUDY DESIGN

No text is to be entered in this section; rather it should be included under the relevant subheadings below.

4.1 OVERALL DESIGN

This is a Phase II single-site randomized, 2-arm between-subjects study examining differences in diabetes risk and knowledge between participants randomized to the experimental intervention and those randomized to the attention control condition (usual care). Outcomes were assessed at baseline, three months 1 week post baseline, and again at 6-months 1 week post-baseline. We hypothesized that experimental participants would have higher rates of percent weight loss and improved knowledge and behaviors to reduce diabetes risk than control participants. Participants were assigned to conditions by an algorithm programmed into the study computer using a permuted blocks randomization scheme. Blocks of size 4 and 6 were used. Assignments within blocks were to be random but balanced among the two conditions and the order of the blocks (4 vs 6) also was random. This procedure will ensure that the number of participants randomized to each condition was equal, that any imbalance among the conditions at any point during the recruitment and randomization was modest, and that it would be very difficult to guess the assignment of the next participant. Randomization was administered via computer-based admin system and triggered by the study coordinator.

The intervention, STEPS, combines educational videos and content, as well as skill development exercises to provide diabetes education, reduce risk of developing Type II Diabetes.

4.2 SCIENTIFIC RATIONALE FOR STUDY DESIGN

Those in the control condition will receive UC. Due to the lack of adequate resources for T2D prevention in rural communities,⁶²⁻⁶³ we designed the control to provide the most intensive diabetes prevention education a patient could expect from their primary care doctor.^{118,149} This method has been used in prior RCTs examining the effects of T2D prevention programs for Hispanic adults.^{118,149} This study design was chosen to allow for a comparison between the STEPS intervention and what is commonly available to Hispanics in rural areas.

4.3 JUSTIFICATION FOR INTERVENTION

The STEPS intervention is an effective, affordable, and scalable intervention to reduce diabetes risk among Hispanic adults. Principles from the Social Cognitive Theory (SCT),^{53,84,117} Theories of Social Networks and Social Support¹¹⁷ will guide development of **STEPS**. For example, self-regulation is a core concept of SCT¹¹⁷ and a key component of T2D prevention.⁹⁸ As such, **STEPS** will include interactive tools to help end-users set PA and eating goals, monitor progress towards meeting those goals, and reinforce success through feedback. Additionally, outcome expectations related to T2D diagnosis and outcomes will be examined through a cultural lens. There will be substantial observational learning opportunities through videos and interactive activities that will also reinforce self-efficacy in healthy eating and PA. Additionally, the Theories of Social Networks and Social Support¹¹⁷ will provide a framework to mobilize social resources at both the individual and community levels. Our tool, Connect with Comadres/Compadres, will encourage social network appraisal and help users solicit instrumental support to meet their health goals. Lastly, the FiLLM⁵⁰ model will guide cultural tailoring of **STEPS** to meet the needs of rural Hispanics.

4.4 END-OF-STUDY DEFINITION

A participant is considered to have completed the study if he or she has completed the baseline assessment and the 6-month follow-up assessment.

5 STUDY POPULATION

5.1 INCLUSION CRITERIA

In order to be eligible to participate in this study, an individual must meet all of the following criteria:

1. Provision of signed and dated informed consent form
2. 18 years of age and older

3. Able to read and write in English or Spanish
4. Hispanic
5. Resides in rural area
6. Has access to a smartphone and internet access
7. Does not have diabetes
8. Has prediabetes as per screener
9. Not currently pregnant
10. Can participate in physical activity as per screener

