While the blood sample is just a droplet of blood, there might be participants who have anxiety about blood and/or may feel light-headed at the sight of blood. Therefore, all participants will be required to be seated while they conduct the self-test. Additionally, if a participant feels unwell due to the blood

droplet, ISA STAFF will immediately call CACOST Health Center Staff to come assess the participant. While highly unlikely, in the case that there is a medical emergency, ISA Staff will immediately contact first responders. After the incident has been handled and cleared, ISA Staff will immediately contact the PI to inform them of the event and will document details.

Additionally, there may be associated risks with the participant learning their A1C levels. If a participant's A1C level is in the diabetes range, they will be provided with a sheet with information on A1C levels and information about how to contact their primary care physician about their results. This sheet will provide CACOST Health Center contact information as well.

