5.2 EXCLUSION CRITERIA

An individual who meets any of the following criteria will be excluded from participation in this study:

1. Less than 18 years of age
2. Not able to read and write in English or Spanish
3. Resides in a metropolitan area
4. Does not have access to a smartphone and internet
5. Has been diagnosed with diabetes
6. Cannot participate in physical activity as per screener

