8.1 ENDPOINT AND OTHER NON-SAFETY ASSESSMENTS

This individually randomized, remote trial evaluates a mobile, web app diabetes prevention program versus a usual care control. All study activities are conducted in person with a trained research coordinator. The research coordinator obtains only weight and instant A1C measures if participant has agreed to the measures, and the remaining data is collected via a participant initiated questionnaire.

Screening, eligibility, and enrollment

- **Eligibility confirmation window.** Up to 30 days prior to enrollment. Research coordinator assesses eligibility and pending eligibility (from physical activity readiness questionnaire). For those with pending eligibility, the research coordinator must receive a doctor's signed form allowing participation in physical activity for the study.
- **Consent.** Participants complete electronic informed consent.
- **Baseline survey.** Immediately post-consent, participants complete a baseline questionnaire.
- **Randomization.** After baseline completion, participants are assigned to intervention or control.

Interventions begin (initial administration conditions)

- **Intervention arm.** Participants are told to immediately wear their fit bit for one week to get baseline physical activity measure. One week post baseline visit, they are provided their username and password to login and commence the intervention.
- **Control arm.** Participants are told to immediately wear their fit bit for one week to get baseline physical activity measure. They are also told they are in the usual care group and will receive access to the intervention post-study.

Measures and assessments (non-safety)

Baseline (pre-randomization)

- Demographics and contact details (mobile number required for delivery).
- Diabetes knowledge questionnaire
- Health behavior questionnaire
- A1C and weight biometrics

During intervention (process/dose)

- The administrative platform will provide all utilization details including login, page numbers, minutes used, and additional utilization statistics. These are used for exposure/dose summaries and adherence monitoring (not safety).

Follow-up (primary outcome window)

- **Primary outcome ascertainment:** Weight measure is utilized for future calculation of percent weight loss.
- **Follow-up questionnaire:** Repeat weight measurement at each follow up visit is used for percent weight loss.

Outcome definitions (non-safety)

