8.2 SAFETY ASSESSMENTS

The current study gathered two biometric data points: (1) weight and (2) A1C levels using a rapid at-home assessment. Given the A1C test, the study followed the following protocol.

A1C Protocol for Safety Assessment. There are some minor health risks associated with conducting and obtaining information from a rapid A1C test. The use of a rapid A1C test is no more of a risk than using a blood glucose meter. It does not require blood to be drawn, in large amounts, or using a syringe. It also does not require a medical professional to complete. An A1C self-check will be conducted by the participant after being provided with instructions by ISA Staff. ISA Staff will monitor to ensure the participant is following directions. This test requires a droplet of blood only slightly larger than a traditional glucose monitor test. Participants will do the step-by-step instructions and then show ISA Staff their A1C reading. If a participant does NOT want to participate in doing the test, they will not be required to. There are minimal risks associated with the test. To alleviate the risks, ISA Staff will implement the following procedures for the following associated risks.

First, even though ISA Staff will be instructing the participant to self-test, they will wear a new set of latex gloves with each reach in the case they need to assist the participant. They will also throw all supplies in a sharps container once the test is completed. They will disinfect the area where the test is conducted as well.

While the blood sample is just a droplet of blood, there might be participants who have anxiety about blood and/or may feel light-headed at the sight of blood. Therefore, all participants will be required to be seated while they conduct the self-test. Additionally, if a participant feels unwell due to the blood

droplet, ISA STAFF will immediately call CACOST Health Center Staff to come assess the participant. While highly unlikely, in the case that there is a medical emergency, ISA Staff will immediately contact first responders. After the incident has been handled and cleared, ISA Staff will immediately contact the PI to inform them of the event and will document details.

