Additionally, there may be associated risks with the participant learning their A1C levels. If a participant's A1C level is in the diabetes range, they will be provided with a sheet with information on A1C levels and information about how to contact their primary care physician about their results. This sheet will provide CACOST Health Center contact information as well.

Further safety procedures consist of: (1) AE/SAE identification and follow-up; (2) monitoring for distress potentially triggered by educational content; (3) privacy/technology safeguards (e.g., wrong-number texting, shared phones). AEs are any unfavorable or unintended psychological or practical effect temporally associated with participation in the study's activities (videos, , surveys), whether or not considered related. Examples include: heightened anxiety/distress about diabetes risk, perceived breach of privacy (e.g., texts seen by others on a shared device), escalation of medical mistrust that prompts clinical concern, and elevated A1C measures that require further doctors assessments. SAEs would be rare in this context and are defined per IRB policy (e.g., death, life-threatening event, hospitalization) regardless of attribution.

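### No step says whether the A1C read before randomisation is used to apply the no-diabetes criterion, and the A1C analysis neither names baseline A1C as a covariate nor examines participants who start in the diabetes range

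*Combined protocol and SAP*

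**What the plan says.** **Eligibility.** Inclusion criterion 7 in 5.1 is "Does not have diabetes", with no method of confirmation. Criterion 8 is "Has prediabetes as per screener". Exclusion criterion 5 in 5.2 is "Has been diagnosed with diabetes". No A1C cut-off appears anywhere.

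**Timing.** Section 8.1 lists "A1C and weight biometrics" among the baseline measures taken before randomisation, and then states: "After baseline completion, participants are assigned to intervention or control". No eligibility check is described between the two. Eligibility is confirmed earlier, at pre-screening (1.3 and 8.1).

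**Response to a high reading.** Sections 2.3.1 and 8.2 say that if a participant's "A1C level is in the diabetes range, they will be provided with a sheet with information on A1C levels" and on how to reach a physician. Section 8.2 also gives elevated A1C needing a doctor's assessment as an example of an adverse event. Section 8.3.4 has adverse events recorded and followed, and 7.1 has the investigator or a designee consider clinically significant findings after enrolment.

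**Optional test.** Section 8.2 says: "If a participant does NOT want to participate in doing the test, they will not be required to".

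**Analysis.** Section 9.3 keeps everyone randomised in all analyses. Sections 9.4.1 to 9.4.3 refer to an adjusted difference between conditions without naming covariates. Section 9.4.5 adjusts for variables that differ between groups at p < .10. Sections 9.4.7 and 9.4.9 plan nothing by baseline A1C, and 6.5 (concomitant therapy) is marked not applicable.

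**The concern.** The synopsis describes the population as adults with prediabetes. The protocol expects some diabetes-range readings, since it sets out a procedure for them, and it points those people towards medical care. If such a reading comes before randomisation and no step ties it to criterion 7, staff can randomise the person in good faith.

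Three things follow. The population to which the conclusion applies becomes unclear. The A1C endpoint at 3 and 6 months (9.1) may be noisier, because a few participants may start higher and change by different amounts. And with few such people, an uneven split between arms can shift the A1C comparison by chance. The plan has no tool aimed at any of this: baseline A1C enters the model only if it happens to differ at p < .10, and no analysis shows how far the result depends on these participants. With concomitant therapy not applicable, the plan also states no record of treatment begun after such a reading, which could affect weight as well as A1C.

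**Working it through.** **The plan's own figure.** The documents give no power figure, SD or effect for A1C, and no expected share in the diabetes range. The only sample-size figure is 136 evaluable participants for weight loss (9.2), or 68 per arm. That number reproduces as a one-sided two-sample t-test with d = 0.43 and 80% power. The declared two-sided test would need 172, which is a separate matter. Here 68 per arm serves only as the evaluable number.

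**Inputs for A1C (all assumed except n and alpha).** n = 68 per arm; two-sided 5% test (9.4.2); SD of A1C change in the prediabetes range s0 = 0.25, with mean change taken as 0; true between-arm effect 0.12, the same for everyone; share p with diabetes-range baseline A1C of 2%, 5% or 10% (about 3, 8 or 16 of the 164 to be randomised); mean change m and SD s1 in that subgroup as tabled.

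**Formula.** Total variance = (1 − p)·s0² + p·s1² + p(1 − p)·m². Power is that of a two-sample t-test on 0.12 divided by the total SD.

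Example, p = 5%, m = −1.0, s1 = 1.0: 0.95 × 0.0625 + 0.05 × 1 + 0.05 × 0.95 × 1 = 0.0594 + 0.0500 + 0.0475 = 0.1569, so SD = 0.396 and power = 42%.

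| Subgroup assumption | SD at 2% / 5% / 10% | Power at 2% / 5% / 10% |
|---|---|---|
| No subgroup | 0.25 | 79% |
| m = −0.2, s1 = 0.3 | 0.253 / 0.256 / 0.262 | 78 / 77 / 75% |
| m = −0.5, s1 = 0.6 | 0.271 / 0.299 / 0.339 | 73 / 64 / 54% |
| m = −1.0, s1 = 1.0 | 0.318 / 0.396 / 0.496 | 59 / 42 / 29% |

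**What baseline adjustment could recover.** In the best case, adjusting for baseline A1C removes the mean-shift term p(1 − p)·m². Power is then 76 / 71 / 63% in the middle row and 68 / 56 / 42% in the last row. Part of the loss is recovered. The rest comes from the subgroup's larger residual spread.

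**What the sensitivity set costs.** Dropping 2%, 5% or 10% leaves about 66.6, 64.6 or 61.2 per arm. With SD 0.25, power is 79 / 77 / 75%.

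**Chance imbalance.** With 16 such people among 164 split 82/82 by simple allocation, the probability that the arms differ by 4 or more is about 43%; with 8 it is about 28%. If those people sit 1.5 A1C points higher (assumed), a difference of 4 shifts the unadjusted A1C comparison by about 4/82 × 1.5 = 0.07 points, against the assumed effect of 0.12.

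**The case against.** **The two lists do not truly conflict.** A reader might infer that 5.1 and 5.2 set contradictory rules. They do not: every inclusion criterion must be met, so criterion 7 binds whatever 5.2 says. The exclusion list is a partial restatement, which also omits ethnicity, prediabetes, pregnancy and consent. This stands. The gap is that no step applies criterion 7 to the A1C reading.

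**Nothing says such people are randomised.** That they certainly are is another tempting inference. Section 5.4 defines screen failures as people who consent but are not then assigned, which covers the interval in which A1C is read. Section 7.2 allows discontinuation for ineligibility found after enrolment. This too stands, so the supportable statement is that they can be randomised. Neither route names A1C.

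**The sheet is not the only response.** Sections 7.1, 8.2 and 8.3.4 add adverse-event recording and follow-up and investigator review. That is correct, but none of it settles eligibility or the analysis.

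**The size is assumed.** A reader might infer that a handful of such participants would dominate the A1C result. The documents give no SD, share or expected change to support this, and with a mild subgroup the loss is 1 to 4 percentage points of power. The severe figures also come from an unadjusted analysis, whereas 9.4.1 speaks of an adjusted difference. This limits the claim to a range. It does not answer the point that the adjustment leaves baseline A1C unnamed.

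**A1C is secondary.** The trial is sized on weight, no effect on weight is quantified here, and no bias or false-positive risk is shown. This stands, and it bounds the importance of the point.

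**Conclusion.** The concern holds in a limited form. The protocol reads A1C before randomisation and bars diabetes, but does not say whether the one is used to apply the other. People with a diabetes-range A1C can therefore enter, and intention-to-treat keeps them in.

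The consequences are possible loss of precision and chance imbalance on a secondary endpoint, and a less clearly defined population. Systematic bias between arms is not among them. For a 2-10% share, power on A1C could fall from 79% to anywhere between 78-75% and 59-29%. That range rests wholly on the assumed SD of 0.25, effect of 0.12, subgroup share and subgroup change. It shows that the matter could be trivial or substantial, not which.

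The eligibility wording alone would be only a clarification. What makes the point worth acting on is that the analysis can be improved with data the trial already plans to collect.

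**What to change.** 1. In 9.4.3, name baseline A1C as a covariate in the A1C analysis whatever the baseline balance, replacing the p < .10 rule in 9.4.5 for this outcome.
2. Pre-specify a sensitivity repeat of the A1C and weight analyses without participants whose baseline A1C was in the diabetes range, using a cut-off that the sponsor states in advance. Report the number of such participants by arm. The intention-to-treat analysis stays the main one.
3. Reconcile 5.1, 5.2, 8.1 and 8.2 on whether the pre-randomisation A1C bears on eligibility, and on what applies when the test is declined. The clinical rule is for the sponsor to set.

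**Cost.** Some wording and one extra analysis, with no new measurement; items 1 and 2 remain possible after enrolment is complete. The sensitivity set is slightly smaller. Because the test is optional, a few participants cannot be classified, or will need an imputed baseline value for the covariate. The plan should say how each is handled.
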